1.6 Rationale for the Recommended Phase 2 Dose Selection

The selection of the recommended phase 2 dose (RP2D) was based on the review of the totality of available data including, but not limited to, the observed safety, tolerability and preliminary clinical activity of AFM24 as well as the available PK and pharmacodynamic (PD) data for AFM24. A brief summary of the data and the RP2D selection is provided below. Please refer to the Investigator's Brochure for more details.

As of a data cutoff date of 29 October 2021, 29 subjects were enrolled into 6 dose cohorts, with AFM24 doses ranging from 14 mg to 480 mg i.v. every 1 week (q1w). AFM24 was generally safe and well tolerated across dose levels, with infusion-related reactions (IRRs) (69%) being the most frequently reported treatment-emergent adverse events (TEAEs). There were no treatment-related deaths. No dose-limiting toxicities (DLTs) were observed in 6 subjects at the highest dose of 480 mg.

Best objective response (BOR) per Response Evaluation Criteria in Solid Tumors (RECIST) v1.1 was stable disease (SD) in 8 of 24 response-evaluable subjects.

At 480 mg, dose proportional PK was reached, suggesting a peripheral saturation of target (EGFR)-mediated elimination. The preliminary exposure-response curve with CD16a RO appeared to level off to approximately 30-40% RO at concentrations that were reached with 480 mg, indicating that higher exposures would not lead to higher CD16a RO. Moreover, estimated intra-tumoral AFM24 concentrations and CD16a RO were in the range associated with maximum tumor cell killing (SW-982 cells or A-431 cells) *in vitro* (Affimed Study No. AFM24_018).

Taken together, based on the review of the totality of available data, the Safety Review Committee (SRC) (Section 3.6) determined 480 mg i.v. q1w as an acceptable RP2D of AFM24. The Phase 1 part of the study was ongoing at the time of selection of this RP2D and Cohort 7 (720 mg q1w) had been opened for enrollment.

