3.4.1 Definition of Maximum Tolerated Dose

The MTD is defined as the highest dose of AFM24 if both of the following criteria are fulfilled:

- The posterior probability of the true DLT rate being in the target interval ($\geq 16\%$ to $<33\%$) is $>50\%$ with less than 25% risk of the true DLT rate being above 33%; and
- At least 6 subjects have been treated at that cohort in the first cycle of AFM24 treatment under that dosing schedule.

As described in Section 3.4.3, an RP2D can be declared if:

- The MTD criteria are not met on any dose level and/or clinical and laboratory data indicate an optimal biologically active dose has been reached (with less than 25% risk of the true DLT rate being above 33%).

AND

- At least 6 subjects have been treated at that dose level.

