3.4.2 Definition of Dose-Limiting Toxicity (DLT)

Dose-limiting toxicity is defined as an AE or abnormal laboratory value assessed as unrelated to underlying disease, disease progression, inter-current illness, or concomitant medications, that occurs ≤ 28 days following the first dose of AFM24 (Cycle 1) and that meets any of the following criteria shown in Table 3. Clinically relevant toxicities will be evaluated according to the National Cancer Institute (NCI)/National Institutes of Health CTCAE v5.0. Subjects who experience a DLT during Cycle 1 must permanently discontinue AFM24.

Subjects must receive $\geq 80\%$ of their assigned AFM24 dose in Cycle 1 and complete the 28-day DLT observation period or have had a DLT within the first cycle of treatment to be considered evaluable for DLT.

For dose-escalation decisions, only DLTs occurring during Cycle 1 of treatment will be considered in the 2-parameter BLRM.

Table 3: Definition of Dose Limiting Toxicity

Toxicity	Any of the following criteria
Hematological ^a	\geq CTCAE Grade 4 neutropenia (ANC $<0.5 \times 10^9/L$) lasting for longer than 4 consecutive days
	Febrile neutropenia (ANC $<1.0 \times 10^9/L$ of any duration accompanied by fever $\geq 38.5^\circ C$ or systemic infection)
	CTCAE Grade 3 thrombocytopenia (platelets 25 to $<50 \times 10^9/L$) associated with bleeding
	CTCAE Grade 4 thrombocytopenia (platelets $<25 \times 10^9/L$)
	\geq CTCAE Grade 4 anemia that is considered to be treatment related
Non-hematological	
Any \geqCTCAE Grade 3 AE including, but not limited to:
 
• CTCAE Grade 3 infusion-related reaction/cytokine release syndrome not responsive to symptomatic treatment within 6 hours (ie, no improvement to Grade 2 or better within 6 hours with optimal medical management)• CTCAE Grade 4 infusion-related reaction/cytokine release syndrome• QTcF prolongation (>500 msec)

Toxicity	Any of the following criteria

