	
 CTCAE Grade 3 hypertension for >14 consecutive days despite optimal anti-hypertension therapy CTCAE Grade 4 hypertension ≥CTCAE Grade 3 total bilirubin (>3×ULN) ≥CTCAE Grade 3 ALT, AST, or ALP (>5×ULN) Subjects without hepatic metastasis: subjects fulfilling Hy's law criteria or 1.5 times increase from baseline value of total bilirubin for >2 weeks^b; Subjects with hepatic metastasis: 1.5 times increase from baseline value of total bilirubin for >2 weeks^b; ≥CTCAE Grade 3 vomiting or nausea for ≥72 hours despite optimal anti-emetic therapy; and/or ≥CTCAE Grade 3 diarrhea for ≥72 hours despite optimal anti-diarrhea treatment
	Any other ≥CTCAE Grade 3 AE not listed above, except for the exclusions noted below
	Inability to receive at least 3 of the scheduled doses of AFM24 in Cycle 1 due to treatment-related toxicity
	
Any other toxicity (irrespective of grade) that:
 
 Is greater than that at baseline and clinically significant and/or unacceptable and/or does not respond to supportive care and judged to be a DLT by the SRC; or Results in a disruption of AFM24 dosing for more than 2 weeks
Exceptions to DLT criteria ^c	Isolated laboratory changes of any grade without clinical sequelae or clinical significance with the exception of those laboratory changes outlined above
	CTCAE Grade 3 fever (in the absence of neutropenia) or fatigue that resolves to <Grade 3 within 72 hours
	CTCAE Grade 3 hypertension for ≤14 consecutive days
	CTCAE Grade 3 nausea, vomiting, diarrhea, or dehydration that resolves to <Grade 3 within 72 hours of initiating optimal supportive care treatment
	CTCAE Grade 3 infusion-related reaction/cytokine release syndrome responsive to symptomatic treatment within 6 hours (ie, improvement to Grade 2 or better within 6 hours with optimal medical management)

AE = adverse event; ALT = alanine aminotransferase; ALP = alkaline phosphatase; ANC = absolute neutrophil count; AST = aspartate aminotransferase; CTCAE = Common Terminology Criteria for Adverse Events; DLT = dose-limiting toxicity; NCI = National Cancer Institute; QTcF = corrected QT interval by Fridericia; SRC = Safety Review Committee; ULN = upper limit of normal.

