5.2 Study Drug Administration

All doses of AFM24 will be administered as an i.v. infusion. During the dose escalation phase (Phase 1), subjects will receive AFM24 as a weekly infusion. As mentioned in Section 3.1, additional dosing regimen (i.e., q2w) may be explored in the dose expansion phase (Phase 2a) **only**.

For dose escalation phase (Phase 1) and dose expansion phase (Phase 2a)

- Weekly dosing regimen (q1w): i.e., on Day 1, Day 8, Day 15, and Day 22 of a 28-day cycle (see APPENDIX A [Section 14.1]).

For dose expansion phase (Phase 2a) only

In addition to the weekly dosing regimen mentioned above, the following dosing regimen may be used:

- Every-2-weeks dosing regimen (q2w): i.e., on Day 1 and Day 15 of a 28-day cycle (see APPENDIX B [Section 14.2]). If the drug is given on a q2w schedule, the daily dose will not be higher than the highest daily dose that was tested in Phase 1 part of the study and was considered safe.

The baseline infusion time should not take less than approximately 4 hours for at least the first 2 AFM24 infusions (**Note:** infusion time is approximately 4 hours, any infusion time \geq 3 hour 50 minutes will not be a deviation). It should also be noted that as the dose escalation continues into the higher dosing cohorts, the baseline infusion time may increase to >4 hours and as long as over 2 days (ie, split day dosing) based on a given subject's tolerability as detailed in the Pharmacy Manual for each cohort. For infusion times that span over 2 days (i.e., split day dosing), timepoints for different assessment may be affected and the Schedule of Assessment (SoA) tables should be referenced for details (See Section 14.1 and Section 14.2 for SoA tables

for weekly and q2w dosing schedules, respectively). If the first 2 consecutive AFM24 infusions are well tolerated (defined as no IRR/cytokine release syndrome (CRS) Grade >1), then the infusion time may be decreased to <4 hours to a minimum of 1 hour starting with the third subsequent infusion (ie, C1D15 for weekly dosing regimen and C2D1 for q2w dosing regimen) at the discretion of the Investigator along with a potential reduction of post infusion- observation period (with regular checks of vital signs, please refer to [Table 5](#) for detailed description) from 4 hours to a minimum of 2 hours and a taper of corticosteroid premedication. Investigators should only make 1 modification per infusion at 1 time.

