5.4 Dose Interruptions or Delays

AFM24 dosing delays may be permitted in the case of medical/surgical events or logistical reasons not related to study therapy (e.g., elective surgery, unrelated medical events, subject vacation and/or holidays). Subjects should re-commence study therapy within 3 weeks of the interruption, unless otherwise discussed and agreed with the Sponsor. Every effort should be made to avoid dose delays during the DLT observation period (Cycle 1 of the dose escalation phase).

Dose delays of up to 3 weeks (≤ 21 days between 2 consecutive doses) are allowed for subjects to recover from any AE and return to baseline or Grade ≤ 1 (except for fatigue or anorexia).

Subjects who do not recover from any AE and return to baseline or Grade ≤ 1 (except for fatigue or anorexia) within 3 weeks (≤ 21 days between 2 consecutive doses) must discontinue AFM24 permanently.

Please refer to APPENDIX A (Section 14.1) and APPENDIX B (Section 14.2) for more details of weekly and q2w AFM24 dosing schedules, respectively.

Weekly dosing schedule:

If the subject recovers from an AE and is able to continue study drug within 72 hours of the originally scheduled dosing day, then the subject should receive the delayed dose and continue treatment as per the original schedule, by not shifting any later doses. There should be at least 4 days without treatment before the subject receives the next dose. An example: if the subject has an AE on C1D15 and recovers in time and can receive the missed dose on C1D18, then the next dose for the subject is on C1D22.

If the subject does not recover from an AE within 72 hours, the missed dose(s) should be skipped and the subject should receive the next dose as per original schedule. An example: a missed dose on C2D1 and the subject recovered on C2D9, the next dose for this subject is on C2D15.

Every-2-weeks dosing schedule:

If the subject recovers from an AE and is able to continue study drug within 1 week from the original scheduled dosing day then the subject should receive the delayed dose and continue treatment as per the original schedule, by not shifting any later doses. There should be at least 7 days without treatment before the subject receives the next dose. An example: if the subject has an AE on C1D1 and recovers in time and can receive the missed dose latest on C1D8, then the next dose for the subject is on C1D15.

Further dose delays or skipping is not allowed for subjects to recover from any AE.

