5.8 Management of AFM24-Related Toxicities

Any DLT during Cycle 1 in the Phase 1 part: Permanently discontinue AFM24.

Please see APPENDIX F (Section 14.6) for a summary of management of IRR/CRS, and other AFM24-related AEs.

Fever: Subjects who develop fever during AFM24 treatment should be supported with antipyretic medications such as paracetamol or metamizole-sodium. If the subject develops high fever (above 40°C body temperature) physical cooling of the body, e.g., with cold packs should be considered. AFM24 treatment is recommended to be held for subjects who have body temperature $\geq 38^\circ\text{C}$ until temperature normalizes below 38°C.

Cytokine release syndrome: See APPENDIX F (Section 14.6; grading and management of IRRs, CRS, and other AFM24-related AE) for detailed grading criteria and detailed guidance on management.

Dermatological toxicities: Investigators are asked to pay special attention to ALL dermatological toxicities and consult with a dermatologist if needed. In cases of \geq Grade 3 skin toxicity, AFM24 treatment should be interrupted or postponed until the reaction resolves to \leq Grade 1 or baseline. Subjects should be asked to limit direct sunlight exposure and apply protective sun cream during treatment with AFM24. A rechallenge should be considered at the discretion of the Investigator but AFM24 should be permanently discontinued with a recurrence of Grade 3 skin toxicity.

IRRs: See APPENDIX F (Section 14.6; grading and management of IRs, CRS, and other AFM24-related AEs) for detailed grading criteria and detailed guidance on management.

Electrolyte abnormalities: Consider withholding AFM24 for \geq Grade 2 electrolyte abnormalities and resume when resolved. Replenish electrolytes as medically appropriate.

Pulmonary symptoms: In the event of acute onset or worsening of pulmonary symptoms, interrupt AFM24 therapy. Discontinue AFM24 therapy if interstitial lung disease is confirmed.

Hepatotoxicity: If severe (CTCAE Grade ≥ 3) hepatic impairment develops for subject with/without liver metastasis, AFM24 should be discontinued permanently.

Gastrointestinal Perforation: Permanently discontinue AFM24 in subjects who develop gastrointestinal perforation.

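### A Phase 1 subject who skips exactly one of four Cycle 1 doses for a drug-related AE that is not otherwise a DLT is neither a missed-dose DLT nor evaluable, and so drops out of the DDS and the BLRM for a toxicity-related reason

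*Protocol*

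**What the plan says.** **Schedule.** Protocol 5.2 sets four Cycle 1 infusions: "Weekly dosing regimen (q1w): i.e., on Day 1, Day 8, Day 15, and Day 22 of a 28-day cycle". Phase 1 uses only this schedule.

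**Skip rule.** Under Protocol 5.4 a dose may be given late if the AE recovers within 72 hours. Otherwise, "If the subject does not recover from an AE within 72 hours, the missed dose(s) should be skipped", and dosing resumes at the next scheduled visit. The dose is not made up.

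**Missed-dose DLT.** Table 3 (Protocol 3.4.2) has two lines on lost dosing: "Inability to receive at least 3 of the scheduled doses of AFM24 in Cycle 1 due to treatment-related toxicity", and any toxicity that "Results in a disruption of AFM24 dosing for more than 2 weeks".

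**Evaluability.** Protocol 3.4.2 requires subjects to receive at least 80% "of their assigned AFM24 dose in Cycle 1 and complete the 28-day DLT observation period or have had a DLT within the first cycle". Protocol 9.1 and SAP 6.2 repeat the 80% floor. Only evaluable subjects enter the dose-determining set (DDS), and only the DDS feeds the Bayesian logistic regression model (BLRM).

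**RP2D.** One condition in Protocol 3.4.1 for declaring an RP2D is "At least 6 subjects have been treated at that dose level". It counts treated subjects, not evaluable ones. Section 1.6 reports: "No dose-limiting toxicities (DLTs) were observed in 6 subjects at the highest dose of 480 mg".

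**The concern.** The two rules leave a gap at exactly three of four doses. Four doses is evaluable. Two or fewer because of treatment-related toxicity is a DLT. Three is neither.

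The gap applies only to AEs that are not DLTs on another ground, but the protocol itself holds treatment for some of these. Section 5.8 has a hold for fever ("AFM24 treatment is recommended to be held for subjects who have body temperature" of 38 °C or more), suggests withholding for Grade 2 or higher electrolyte abnormalities, and interrupts for acute pulmonary symptoms. It also interrupts for Grade 3 toxicity that is not a DLT, such as hypertension of 14 days or less, which Table 3 excepts. If such a hold outlasts 72 hours, the dose is lost.

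DLT incidence is the Phase 1 primary endpoint and is analysed on the DDS. Subjects lost this way are lost because of the drug, not at random. The direction of the bias depends on what the subject would otherwise have been: exclusion overstates toxicity slightly against a non-DLT, and understates it against a DLT. From Cohort 3 on, replacement occurs only if fewer than three subjects are evaluable, so a fourth subject can drop out of the model unreplaced.

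**Working it through.** **1. Dose fraction.** Doses received divided by the four scheduled:

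| Cycle 1 doses | Fraction | Missed-dose DLT (if toxicity-related) | At least 80% |
|---|---|---|---|
| 4 | 100% | no | yes |
| 3 | 75% | no | no |
| 2 | 50% | yes | no |

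The floor equals 0.80 × 4 = 3.2 doses. Three infusions would each have to be 3.2/3 = 106.7% of the assigned dose to reach it. With partial infusions the fraction falls below 75%.

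**2. Disruption line.** On nominal days, one skip gives Day 1 to 15, Day 8 to 22, or Day 15 to 29 (Cycle 2 Day 1). Each is 14 days, which is not more than two weeks.

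**3. Model check.** Inputs from Protocol 9.3.4.1 and Table 8: logit p(d) = log α + β log(d/180), log α ~ N(−1.983, SD 2), log β ~ N(−0.217, SD 1), correlation 0. Overdose means a DLT rate of 0.33 or more, and the limit is 0.25. Grid integration (1601 × 1601) against Table 19:

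| Scenario | Dose (mg) | Printed | Recomputed |
|---|---|---|---|
| 8 | 360 | 0.245 | 0.236 |
| 9a | 120 | 0.159 | 0.166 |
| 9b | 200 | 0.217 | 0.213 |
| 12 | 1000 | 0.225 | 0.218 |
| 13 | 360 | 0.280 | 0.281 |

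Agreement is within 0.01.

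**4. Escalation example (assumed data).** 0/2 at 14 mg, 0/2 at 40 mg, then four treated at 120 mg, one of whom skips one dose:

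| Handling | Data at 120 mg | P(overdose) at 360 mg | Model ceiling (5 mg steps) |
|---|---|---|---|
| Excluded (current rule) | 0/3 | 0.236 | 380 mg |
| Non-DLT | 0/4 | 0.221 | 405 mg |
| DLT | 1/4 | 0.490 | 175 mg |

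Protocol 3.4.3 also caps each step at a 200% increase: 120 + 2 × 120 = 360 mg. Excluded or non-DLT, the highest permitted dose is 360 mg. Only counting the subject as a DLT changes it.

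**5. The 480 mg RP2D.** Assume one of the six subjects was such a case. P(overdose):

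| Handling | Data at 480 mg | At 480 mg, 480 mg data only | At 720 mg, 480 mg data only | At 720 mg, adding assumed 0/10 at lower doses |
|---|---|---|---|---|
| Excluded | 0/5 | 0.033 | 0.076 | 0.036 |
| Non-DLT | 0/6 | 0.021 | 0.056 | 0.028 |
| DLT | 1/6 | 0.156 | 0.283 | 0.162 |

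The assumed lower-dose data are 0/2, 0/2, 0/3 and 0/3 at 14, 40, 120 and 360 mg. The actual lower-dose DLT counts are not in the documents.

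**The case against.** The two thresholds answer different questions: whether the dose was too toxic to deliver, and whether exposure was enough to count as tolerating it. They need not meet, and non-evaluable subjects are a category that the protocol foresees and replaces where needed. That stands: no stated figure is wrong. But the third category is here filled partly by drug toxicity, which neither document addresses.

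The affected group is narrow. Most Grade 3 exceptions in Table 3 lapse unless the event improves within 72 hours, and the committee may judge any toxicity to be a DLT. Protocol 3.5 has it weigh all Grade 2 or higher Cycle 1 toxicity, and 5.4 asks for every effort to avoid delays in that cycle. All of this stands and limits the harm. It does not forbid skipping; the sentence in 5.4 barring further skipping follows the every-2-weeks rules, which are Phase 2a only.

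A reader might infer that the CSR would hide these cases. The documents do not support that. SAP 7.8.1 summarizes delays and interruptions with reasons and lists dosing; SAP 7.4 lists study populations. A case could be found by joining listings. What is missing is a stated reason for exclusion from the DDS and any test of its effect on the model.

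A reader might also infer that non-evaluable subjects made up the six at 480 mg. Section 3.4.1 would allow it, but Section 3.6 speaks of expanding to six evaluable subjects, and nothing shows that it happened.

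**Conclusion.** The gap is real and follows from the text: one toxicity-driven skip gives at most 75% against a floor of 80%, is not a missed-dose DLT, and removes the subject from the primary Phase 1 analysis set. This assumes nominal dosing days and an AE that is not a DLT on another ground.

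Its size is modest. Exclusion rather than counting as a non-DLT changes no decision in the worked example. One such subject would not overturn 480 mg under any handling (0.033, 0.021 or 0.156 against 0.25).

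Three stronger readings go beyond the documents. The first is that DLT rates are understated: the bias can run either way. The second is that the 480 mg choice is unsafe: the figures above say otherwise for one subject. The third is that 720 mg would have been barred: that needs the subject counted as a DLT and depends on lower-dose data not given (0.283 or 0.162). How often such skips occurred is not reported. This is an inexpensive improvement to reporting rather than a flaw in the dose selection.

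**What to change.** In SAP 6.2, require a listing of every Phase 1 subject excluded from the DDS with the reason, marking those whose missed dosing was due to toxicity. In SAP 7.7.1, add two reruns of the final BLRM, with toxicity-related exclusions counted once as non-DLT and once as DLT, reported beside the primary DDS result. SAP 7.7.1 already plans predicted DLT and overdose probabilities by dose, so the output format exists. The cost is one listing column and two model runs on data in hand, with no added patients or procedures.

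Rewording evaluability now would come too late to guide the 480 mg choice. If it is changed for any further escalation, lower the floor in Protocol 3.4.2 and 9.1, and in SAP 6.2 and 7.7.1, to at least 75% of the assigned Cycle 1 dose in mg. That meets Table 3's three-dose line. A count of doses received would be looser, because Section 5.4 lets an interrupted infusion be left incomplete and partial infusions could then count as full doses. The downside is that a subject with 75% exposure counts as evidence of tolerability, which slightly eases the model ceiling (380 to 405 mg in the example).

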5.5 Dose Modification

During Phase 1, if a subject is tolerating AFM24 well (ie, no drug-related Grade ≥ 2 toxicity) without evidence of disease progression following 2 cycles, the subject may, beginning with Cycle 3 or a subsequent Cycle, have the dose increased to a dose that has already been established as tolerable by the SRC, and with the agreement of the SRC.

Subjects who experience a DLT during Cycle 1 must permanently discontinue AFM24.

Dose reductions are not allowed.

5.6 Permitted and Restricted Concomitant Medications

5.6.1 Acceptable Concomitant Medications

All treatments and supportive care that the Investigator considers necessary for a subject's welfare may be administered at the discretion of the Investigator in keeping with the standards of medical care of the study site except for the prohibited concomitant medications listed in Section 5.6.2. All concomitant medication will be recorded in the subject's medical records and in the eCRF including all prescription, over-the-counter, herbal supplements, and i.v. medications and fluids. If changes occur during the study period, documentation of drug dosage, frequency, route, and date needs to also be included in the eCRF.

All concomitant medications received from Screening to the Safety Follow-up visit should be recorded as mentioned in the SoA tables (see APPENDIX A [Section 14.1] and APPENDIX B [Section 14.2]). Concomitant medications administered after the Safety Follow-up visit should be recorded for SAEs which are considered related to study drug (Section 8.1).

